Inferences about a disease state from this study can be derived from several logical approaches. These approaches can be grouped into two categories: (1) those dealing with symptoms which can be used to construct a symptom complex that may represent disease, and (2) those dealing with physical signs which in themselves represent disease. In the former, one can form a subset of individuals that have symptoms (e.g., infertility) and study them during the morbidity and follow-up studies. Focusing on the overall patterns of alleged symptoms and categorizing them into a symptom complex may identify those individuals with a disease syndrome, or those at higher risk of developing disease (e.g., genetic disorders, cancer). In the latter approach, data on abnormal physical signs (e.g., genetic defects in offspring) and laboratory results can be compared between exposed and non-exposed groups in an attempt to again establish the presence or absence of disease. By putting this array of data into a logical decision-making scheme, specific relative risks can be calculated in the follow-up study.

FIGURE 5

CONTROL REPLACEMENT FOR THE MORBIDITY AND FOLLOW UP STUDIES

● QUESTIONNAIRE DATA

* LOSS TO STUDY

○ RECONSTRUCTED DATA

☆ PHYSICAL EXAMINATION DATA

By the use of combinational and correlational analyses, statements about the probability of a disease state, a subclinical state, and over-reporting bias can be attempted. If the development of symptoms in the exposed group is positively correlated with physical findings, and this correlation is absent in the control group, a statement concerning the existence of a possible disease state can be made. By taking these possible combinations of observations and viewing them in the context of associated positive verifiers, negative bias indicators, and positive exposure index, the probability of over-reporting bias acting in these circumstances can be substantially reduced and, as a result, any statement concerning the existence of disease is strengthened. Similarly, if symptoms in the exposed group do not correlate with the development of findings, but are associated with positive laboratory results, a statement concerning the existence of a subclinical disease state can be made. However, if comparisons within the RANCH HAND group reveal a negative correlation between reported symptoms and the presence of abnormal physical signs, then an over-reporting bias and/or subclinical disease state is suggested.

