Another method to assist in the determination of a disease state is the use of normalized exposure index and the application of regression techniques to the resulting curve. If there is a positive correlation between increased exposure and the presence of various abnormal physical signs and/or verifiable symptoms, then a symptom complex or disease syndrome is suggested. Factors suspected of altering the classical dose-response curve include cellular repair mechanisms and the hypothesized release of TCDD from adipose tissue following weight loss. The addition of multivariate techniques to the regression analyses will strengthen statements about the presence of disease. Beyond these pair-wise and group comparisons, newer techniques of pattern recognition, such as Factor Analysis and Cluster Theory, are being considered in order to achieve a more automatic and objective analysis.

The strength of any inferences made from these analyses is dependent upon the statistical power inherent in the study. In addition, due to the possibility of latency being a factor in this study, a negative analysis at any time within the study does not categorically imply lack of disease, since sufficient time for emergence may not have passed.

G. Determinations of Exposure Indices:

(1) Exposure Concepts

A major concern in conducting this study is the lack of accurate exposure data. Although most personnel assigned to RANCH HAND squadrons were undoubtedly exposed to Herbicide Orange and TCDD, the exposures within the group must have varied widely. Exposure to herbicides and TCDD by RANCH HAND personnel occurred almost daily. Anecdotal information suggests that many had direct skin contact which was repetitive over a long period of time

(one-year tour for most individuals). Further, it is also suggested that most RANCH HAND personnel felt that the herbicides employed in the operations were not toxic to animals and man and hence, they did not exercise the caution in handling these chemicals that is recommended today. Several individuals have, in fact, repetitively tasted or drunk Herbicide Orange to convince their colleagues or the press of its safety.

From a historical review of RANCH HAND operations, most individuals can be classified into one of three groups based on their likely potential for exposure to the herbicides:

- | | |
|--|--------------------|
| (1) Pilots, Co-pilots and Navigators: | low potential |

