28 NOV 1979

AIR FORCE WORKING PAPER

DESIGN SCHEMATIC

Let f_{RS} be the rate of physical findings among RANCH HAND personnel with findings by questionnaire and let $f_{R\bar{S}}$ be the rate of physical findings among RANCH HAND people with no findings on their questionnaire. For most disease processes it would be expected that f_{RS} should be a larger rate than $f_{R\bar{S}}$. If f_{RS} is observed to be equal to or less than $f_{R\bar{S}}$, an interpretation of over-reporting may be warranted, although the possibility of sub-clinical disease is recognized. Rates f_{CS} and $f_{C\bar{S}}$ will also be estimated, and comparisons between f_{RS} , f_{CS} , $f_{R\bar{S}}$ and $f_{C\bar{S}}$ will be accomplished.

The eight rates m_R' , m_C' , s_R , s_C , f_{RS} , $f_{R\bar{S}}$, f_{CS} , $f_{C\bar{S}}$ and their refinements fully characterize this study. As depicted in Figure 6, "vertical comparisons of these rates provide relative risks m_R'/m_C' , s_R/s_C , f_R/f_C , f_{RS}/f_{CS} and $f_{R\bar{S}}/f_{C\bar{S}}$ which are of central importance in defining herbicide effects. "Horizontal comparisons" relate f_R to s_R , f_{RS} to $f_{R\bar{S}}$, f_C to s_C and f_{CS} to $f_{C\bar{S}}$. Specifically, the ratio f_R/s_R is the ratio of physical findings to reported symptoms in the RANCH HAND population. This ratio may be contrasted with the ratio f_C/s_C and if f_R/s_R is less than f_C/s_C overreporting can be inferred. Likewise, if f_{RS} is less than $f_{R\bar{S}}$, over-reporting is further suggested. A comparison of $f_{RS}/f_{R\bar{S}}$ to $f_{CS}/f_{C\bar{S}}$ contrasts the odds of findings given symptoms in the RANCH HAND population with the odds of findings given symptoms in the control group. If these odds are lower in the RANCH HAND group, over-reporting is again implied. However, the existence of sub-clinical disease as the cause of these ratios cannot be excluded.

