Power calculations are displayed in Table 11. Study power in the case of a matched pair design is strongly dependent on the degree of positive correlation produced between the involved groups by the matching procedure. Of course, the degree of correlation can be expressed by the correlation coefficient r which can take values between -1 (negative correlation) and + 1 (positive correlation), and two values of r have been employed in Table 11. From this table it is seen that if only 450 pairs are studied a 1% shift in mean (= 1.01) will not be reliably detected, but a 2% shift will be detected with a probability of 0.88 if r = 0.2 at least. From this calculation one can infer the need to examine at least 450 pairs to obtain the 2% shift, and to strive for more if possible.

(2) Power in the Dichotomous Variable Case. There is significant discussion in the mathematical statistics literature concerning the efficacy of paired designs in the setting of dichotomous responses (Billewicz, 1974; Ury, 1975; Miettinen, 1970; and several others). Table 12 shows a set of calculations which are applicable to the present study.

TABLE 12

POWER CALCULATIONS FOR THE DICHOTOMOUS VARIABLE CASE AS A
FUNCTION OF EFFICACY OF PAIRED DESIGNS

				POWER = 1 - β		
P_1	P_2	Rel. Risk	r	n=250	n=350	n=450
.05	.01	5	0	.77	.82	.92
.04	.01	4	0	.61	.75	.85
.03	.01	3	0	.40	.51	.59
.10	.05	2	0	.61	.75	.85
.20	.10	2	0	.87	.94	.97
*						
.05	.01	5	.1	.89/.029	.94/.032	.98/.064
.04	.01	4	.1	.72/.033	.87/.038	.88/.041
.03	.01	3	.1	.38/.020	.68/.046	.71/.077
.10	.05	2	.1	.76/.055	.85/.048	.88/.048
.20	.10	2	.1	.94/.043	.98/.046	.99/.057
**						

* $\alpha = .050$ **** α as indicated

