and α and β were obtained from the data. The function represents a fairly high rate disease in that at 40 years of age 7% of the group had the lesion and at 60 years of age 20% had the lesion. The coefficient γ , represents the exposure effect. Power calculations for $\gamma = \beta$ and $\gamma = .8\beta$ are shown in Table 13. This figure suggests that if, as a cell toxin, herbicide exposure accelerates cardiovascular disease, this study has a good chance of detecting that acceleration if the herbicide effect is comparable to the age effect. A slight beneficial effect of pairing is seen in this hypothetical example.

Cancer. A logistic risk function was fitted to breast cancer data presented by Breslow and Day (1975). The function fitted represents a low rate disease in that at 35 years of age only .000336 of the group had the lesion while at 70 years of age .00676 of the group will have the lesion. Using pairing to achieve a power of 0.80 in this setting, 1312 pairs would be needed, when the exposure effect is equal to the age effect. This exceeds the size of our RANCH HAND cohort, and reinforces the fact that herbicide exposure effects on rarer diseases will not have a high likelihood of being detected by this study, and again supports an attempt to examine as many pairs as possible.

TABLE 13

POWER CALCULATIONS AS A FUNCTION OF HERBICIDE EFFECT

ASSUMPTION: $\alpha = 0.05$

Number of Pairs	$\gamma = \beta$		$\gamma = .8\beta$	
	Power Neglecting Pairing	Power With Pairing	Power Neglecting Pairing	Power With Pairing
100	.93	.93	.64	.53 ($\alpha = .036$)
160	>.97	.98	.81	.82
200	>.99	>.995	.86	.87
250	>.99	>.995	.93	.95
300	>.99	>.995	.96	.97
350	>.99	>.995	.97	.98

G. Multivariate Analysis

Some questionnaire and physical examination data naturally fall into groups; for example, fertility/reproduction data, liver function tests, cardiovascular examination tests. In these cases, multivariate analysis may be in order. When the response variables are continuous, they will be analyzed by the well known multivariate extensions of the generalized linear model.

The general approach to multivariate analysis of polytomous data considers all classification factors and all variables as "factors" in a multi-way contingency table. Log-linear models as described above for polytomous data will be employed where appropriate.

H. Indices and Estimates of Exposure

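### Section V.F(2) bases a statement of possible disease on a correlation present in the exposed and absent in controls, without testing whether the two correlations differ

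*Protocol*

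**What the plan says.** Section V.F(2) describes several ways to infer a disease state. One uses the correlation between reported symptoms and physical findings. The condition is: "If the development of symptoms in the exposed group is positively correlated with physical findings, and this correlation is absent in the control group". When it is met, "a statement concerning the existence of a possible disease state can be made". Response verifiers, bias indicators and the exposure index are then brought in; with them, "any statement concerning the existence of disease is strengthened". They add support but are not conditions of the rule.

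The next sentence deals with subclinical disease. A statement is allowed "if symptoms in the exposed group do not correlate with the development of findings, but are associated with positive laboratory results". Controls are not mentioned.

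No test, significance level or definition of absent is given for either sentence. The section closes with a general caution: "The strength of any inferences made from these analyses is dependent upon the statistical power inherent in the study".

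Section VI.A plans a comparison that bears directly on the question. It sets the ratio f_RS / f_R-notS (finding rates in RANCH HAND men with and without symptoms) against f_CS / f_C-notS, and says that this "contrasts the odds of findings given symptoms in the RANCH HAND population with the odds of findings given symptoms in the control group". Only a lower value in RANCH HAND is interpreted, as over-reporting, with subclinical disease not excluded. A higher value is given no meaning, and V.F(2) does not refer to the comparison.

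**The concern.** A correlation detected in one group and not in the other does not show that the groups differ. Section VI.A itself expects that, for most diseases, findings will be more frequent among men with symptoms. Ordinary illness should therefore produce some symptom-finding correlation in controls too. If that correlation is modest, chance alone will often leave it detected in the exposed and undetected in controls.

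The error also runs the other way. If controls show a clear correlation, the condition fails even when the correlation in RANCH HAND men is truly stronger.

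The subclinical sentence is more exposed still, because as written an association found in both groups would satisfy it.

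The stakes are high: section V.F(1) makes determination of disease a main scientific aim, and section III expects the conclusions to bear on compensation.

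**Working it through.** The protocol gives no error rate for this rule, so there is no figure to reproduce.

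**Inputs**
- Group size: 450 per group. Section VI.F(1) says "From this calculation one can infer the need to examine at least 450 pairs", and section VI.A uses one control per exposed man at questionnaire and examination.
- Significance level: 0.05, the level of the power tables in section VI.F. Applying it here, two-sided, is an assumption.
- Absent is read as non-significant (assumption).
- True correlation r: not given in the protocol; varied from 0 to 0.30.
- The two groups' statistics are independent (assumption, relaxed below).

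**Formulas.** By the Fisher z approximation, each group's statistic is normal with standard deviation 1 and mean m = atanh(r) × √(n − 3). For n = 450, √447 = 21.14.
- Two-part rule: P(Z_exposed > 1.96) × P(|Z_control| < 1.96).
- Direct contrast, exposed larger: P(D > 1.96), where D has mean (m_exposed − m_control)/√2 and standard deviation 1.

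**Equal true correlation in both groups, 450 per group**

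| r | m | Exposed positive | Control absent | Rule fires falsely |
|---|---|---|---|---|
| 0 | 0 | 0.025 | 0.950 | 2.4% |
| 0.05 | 1.058 | 0.184 | 0.815 | 15.0% |
| 0.0925 | 1.961 | 0.501 | 0.499 | 25.0% |
| 0.15 | 3.195 | 0.892 | 0.108 | 9.7% |
| 0.20 | 4.286 | 0.990 | 0.010 | 1.0% |

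At r = 0.30 the false rate is about zero. With equal groups the product is close to p(1 − p), p being the within-group power, so it peaks at 0.25 when p = 0.5. Simulation (450 per group, 20,000 runs) gave 2.5%, 25.5%, 9.9% and 1.0% at r = 0, 0.0925, 0.15 and 0.20. The direct contrast gave 2.4% to 2.6% in the same direction at each of these values.

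**Sensitivity of the peak**
- Other sizes: it stays at 25% and moves to r of about 0.124 (250 per group), 0.105 (350) and 0.090 (480).
- One-sided 0.05: also 25%, near r = 0.078 at 450 per group.
- Matching that correlates the two test statistics: 23.4% at correlation 0.1, 21.8% at 0.2.
- Fewer controls than exposed: 30.3% for 450 against 350, 38.2% for 450 against 250.

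**True difference, 450 per group**
- 0.30 exposed, 0.15 control: m = 6.544 and 3.195. Rule: 1.000 × 0.108 = 11%. Contrast: (6.544 − 3.195)/√2 = 2.368; P(Z > 1.96 − 2.368) = 66%.
- 0.15 exposed, 0 control: m = 3.195 and 0. Rule: 0.892 × 0.950 = 85%. Contrast: 3.195/√2 = 2.26; P(Z > 1.96 − 2.26) = 62%.

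**Subclinical sentence, read as needing no control comparison.** Take a symptom-laboratory correlation of 0.15 and a symptom-finding correlation of 0, identical in both groups, with independent tests. Then 0.892 × 0.950 = 85%: the statement would usually be made with no group difference at all.

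**The case against.** The strongest reply is that the sentence is one heuristic among several and does not declare disease. That is right. The text speaks of a possible disease state, invites supporting evidence and ties all such inferences to power. Section V.F(2) also compares signs and laboratory results directly between groups, section VI.A treats the between-group relative risks as central, and exposure-index regression is a further route. A reader might infer that disease is declared by this rule alone, or that the protocol lacks any between-group contrast. Neither is supported.

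A second reply is that definitions of correlated and absent belong in an analysis plan, which is not at hand. This stands for the threshold, and it is why the percentages are conditional. It does not cover the logic. The protocol itself states a comparison of present with absent, and choosing a threshold does not turn that into a test of the difference. The caution about power does not repair this either, and the supporting evidence is directed at over-reporting rather than sampling error.

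Third, the subclinical sentence opens as a parallel to the one before it, so a control comparison may have been intended. That is possible, but it is not written.

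Finally, a reader might multiply the error over every pairing of symptom and measure to forecast many false statements. The protocol does not say that the rule is run on all pairs. At r = 0 the rule (2.4%) and the direct contrast (2.5%) err alike, so such a count would show multiplicity and not this fault.

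**Conclusion.** The concern holds: the correlation-based rule in V.F(2) can turn equal associations into a statement of possible disease, and it can miss a real difference when controls also show a correlation. The false rate reaches about one in four only near 50% within-group power, which is r of about 0.09 with 450 men per group. It is about 2.4% at zero correlation and 1% at r = 0.20. A general 25% error rate would therefore be an over-reading. These figures rest on absent meaning non-significant at two-sided 0.05, equal true correlations, equal group sizes and independent groups. Dependence from matching lowers the peak; fewer controls than exposed raises it above 25%. The subclinical sentence has the same weakness in a stronger form if read literally.

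A reader might also take the three-way term u123 in section VI.D as already the needed test. It is not: that example crosses group, age and retinal grade, with no symptom factor.

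**What to change.** Reword V.F(2) so that the correlation-based statements of possible disease and of subclinical disease each rest on a between-group test that the symptom-finding (or symptom-laboratory) association is larger in RANCH HAND than in controls. Suitable forms are:
- the section VI.A comparison of f_RS / f_R-notS with f_CS / f_C-notS;
- a log-linear model with group, symptom and finding as factors, which the multi-way tables of section VI.G permit;
- for continuous measures, a Fisher z test of the difference between the two correlations.

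In section VI.A, state what a higher value in RANCH HAND means as well as a lower one, and cross-refer the two sections.

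Do not make this interaction a condition for every statement about disease. A herbicide effect that raised symptoms and findings together but left their association unchanged would give no interaction. Keep f_R/f_C, s_R/s_C and the exposure-index regression as separate routes that do not depend on it.

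The cost is small: no new data are needed, but a table with symptom as a factor has to be specified. Where controls truly have no correlation, the difference test has less power than the present rule (62% against 85% in the 0.15 against 0 example).

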This study design incorporates a matched cohort design placed in a non-concurrent prospective setting (incorporating mortality, morbidity, and follow-up studies). Detailed computer searches of Air Force personnel records, with several cross-referencing techniques, will ensure total ascertainment of the RANCH HAND population. Since there was a documented higher concentration of TCDD contamination prior to 1965, this factor will be incorporated in the development of an exposure index. A group of C-130 crewmembers and support personnel will form the control group. They will be matched to RANCH HAND personnel for the variables of age, AFSC, length of time in Vietnam, and race. The ten best matches for each exposed subject will form a control set and they will be randomly ordered. In the analysis of mortality, each exposed subject and a 50% random selection from each control set will be followed yearly. The first of the randomized mortality controls will be selected and entered into the questionnaire and physical examination phases of the study. If this primary control drops out, for reasons other than death, the next control will be selected from the control set so that both statistical power and loss to study bias in the follow-up

study may be improved. All RANCH HAND personnel and their primary controls will be asked to complete a telephone questionnaire and will be offered a comprehensive physical examination, with special emphasis being placed on dermatologic, neuropsychiatric, hepatic, reproductive and neoplastic conditions. An adaptive physical examination and questionnaire will be developed to be used in years three and five of the follow-up study, which is set for a minimum of five years duration. The unusual capabilities of the USAF in the collection, storage, and retrieval of data will allow integration of the various data collection methods used throughout the study. Expected biases and study difficulties include differences in group accountability, risk taking behavior bias in the volunteer RANCH HAND group, response bias, interviewer bias, loss to study difficulties, and variability of procedures performed, as well as the political overlay of this effort.

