II. Synopsis of Background

A. Current

News media presentations have recently focused medical, political and lay attention on possible adverse health effects in military personnel, allegedly due to Herbicide Orange [a mixture of 2,4-dichlorophenoxyacetic acid (2,4-D) and 2,4,5-trichlorophenoxyacetic acid (2,4,5-T)] which was used as a defoliant during the Vietnam Conflict. Other herbicides containing 2,4,5-T were also used extensively, and as commonly used by the news media, the term "Herbicide Orange" refers to all of these 2,4,5-T products (a convention used throughout this protocol). This defoliant was later found to have been contaminated with the toxin 2,3,7,8-tetrachlorodibenzo-p-dioxin (TCDD) (Figure A-1, Section XII). Claims for compensation have been filed against the Veterans Administration (VA), by 650 veterans. In response to Congress, the General Accounting Office (GAO) investigated the issue and subsequently recommended that the Department of Defense (DOD) conduct a long-term epidemiologic study of the problem. The Department of the Air Force has made a formal commitment to the Congress and the White House to conduct such a study.

B. Use of Herbicides

Research and development on phenoxy herbicides began in the early 1940s. Most of the initial phytotoxic screening programs and the development of application technologies were sponsored by the DOD. The herbicide, 2,4,5-T, was first commercially produced in the United States in 1944. During the years from 1961 through 1969, the DOD procured approximately 34 percent of the total US production (53 million pounds) for use in the Republic of Vietnam (RVN). However, 8.9 million pounds of that amount were not sprayed in Vietnam, but were destroyed by at-sea incineration in 1977. The first sustained DOD operational use of herbicides was initiated during the Vietnam Conflict (Operation RANCH HAND) and the first shipment of herbicides used in RANCH HAND was received at Tan Son Nhut Air Base, (RVN), on 9 January 1962. The use of these compounds was intended to accomplish two objectives: (1) the defoliation of vegetation to improve visibility and thus decrease the risk of ambush, and (2) the destruction of enemy crops.

Four 2,4,5-T-containing herbicides were used by the military during the period 1962-1970. These four included:

(1) Herbicide Purple (used from 1962 through 1964)

n-butyl	2,4-D	50%
n-butyl	2,4,5-T	30%
iso-butyl	2,4,5-T	20%

- (2) Herbicide Pink (used from 1962 through 1964)

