 - n-butyl 2,4,5-T 60%
 - iso-butyl 2,4,5-T 40%
- (3) Herbicide Green (used from 1962 through 1964)
 - n-butyl 2,4,5-T 100%
- (4) Herbicide Orange (used from early 1965 through 15 April 1970)
 - n-butyl 2,4-D 50%
 - n-butyl 2,4,5-T 50%

Analyses of archived samples of Herbicide Purple suggest that the mean concentration of TCDD may have been approximately 33 ppm (Range: 17 to 47 ppm TCDD) while archived samples of Herbicide Orange may have had a mean concentration of approximately 2 ppm (Range: <0.02 to 15 ppm TCDD).

In addition, two other herbicides were widely used in RVN. These were Herbicide Blue (an organic arsenical formulated from the sodium salt of cacodylic acid), and Herbicide White (a water soluble triisopropanolamine salt formulation of 2,4-D and picloram). The amounts of the various herbicides used in RVN from January 1962 through February 1972 are shown in Table 1.

Table 1. Estimated Quantities of Herbicides and TCDD Sprayed in RVN, Jan 1962-Feb 1972

CHEMICAL	POUNDS
2,4-D	55,940,150
2,4,5-T	44,232,600
TCDD	368
Picloram	3,041,800
Cacodylic Acid	3,548,710
Herbicide Total	106,763,260

Ninety-six percent of the 2,4,5-T disseminated in RVN was contained in Herbicide Orange; the remaining 4 percent in Herbicides Green, Pink, and Purple. However, Herbicides Green, Pink and Purple contained approximately 40 percent of the estimated amount of TCDD disseminated in RVN. Green, Pink and Purple were sprayed as defoliants on less than 90,000 acres from 1962 through 1964, a period when only a small force of U.S. military personnel were in RVN. Ninety percent of all the Herbicide Orange (containing 38.3 million pounds of 2,4,5-T and 203 lb of TCDD) was used in defoliation operations on 2.9 million acres of inland forests and mangrove forests of RVN.

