| (2) Crew Chiefs, Aircraft Mechanic, and other Support Personnel: | moderate potential |
| (3) Console Operators and Flight Engineers: | high potential |

The "pilot" group probably received most of their exposure during pre-flight checks as well as during the actual dissemination missions. The crew chief group experienced contact with herbicides during dedrumming and aircraft loading operations as well as during on-site repair of the aircraft and spray equipment. The console operator group was exposed while supervising the loading of the aircraft, during ground testing the equipment, and by tank leakage during dissemination missions.

The available historical records on Operation RANCH HAND indicate that personnel assigned to the project seldom had a "routine" work schedule or environment, thus complicating estimates of the level of herbicide and dioxin exposure. Since actual exposure data (e.g., mg of herbicide/kg body wt) are not available, the establishment of an exposure index will be attempted. The exposure index will be calculated for each RANCH HAND individual to obtain a standardized frequency distribution. The exposure index will be calculated by evaluating the known factors that would have influenced exposure. For aircrew members, these will include such factors as:

- (1) Date of tour with RANCH HAND in Vietnam.
- (2) Number and lengths of tours in Vietnam with RANCH HAND.
- (3) Number of herbicide dissemination missions (as reflected by flying hours and air medals).
- (4) Herbicides employed (yearly records are available that reflect the amount of each herbicide sprayed).
- (5) Crew position.
- (6) Routes of exposure (the major route of exposure for most RANCH HAND personnel was probably percutaneous, although for the console operator, exposure through inhalation may have also been significant).

An exposure index may be derived from consideration of the above factors, i.e., it is a function of those factors:

$$E_I = f(D, T, P, C, R, H),$$

where E_I = Exposure Index

D = Dioxin Concentration Estimate During RANCH HAND Tour

The date of tour with RANCH HAND is important since mean dioxin concentrations in the herbicides changed by a factor of 16 between pre-1965 and post-1965. In 1965, both high and low dioxin formulations were available. Thus, a scale of values for TCDD are:

Pre-196532
196516
Post-19652

T = Duration of Exposure/Number of Missions Flown

P = Proportion of 2,4,5-T Herbicides Used

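### The dioxin score of 16 for 1965 has no support in the protocol's own herbicide-use dates, and may be too high by up to 8-fold

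*Protocol*

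**What the plan says.** Section V.G(1), Exposure Concepts, makes the exposure index a function f of six terms. The first, D, is an estimate of the dioxin concentration during a man's tour. It is motivated by the statement that "mean dioxin concentrations in the herbicides changed by a factor of 16 between pre-1965 and post-1965". The scale is 32 for pre-1965, 16 for 1965 and 2 for post-1965. The 1965 value rests on one sentence: "In 1965, both high and low dioxin formulations were available". No shares are given.

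Section II.B, Use of Herbicides, gives the dates of use:

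- "Herbicide Purple (used from 1962 through 1964"
- "Herbicide Pink (used from 1962 through 1964"
- "Herbicide Green (used from 1962 through 1964"
- "Herbicide Orange (used from early 1965 through 15 April 1970"

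The same section repeats the 1962 to 1964 spraying period for Green, Pink and Purple when it gives their acreage. It reports archived-sample means of about 33 ppm TCDD for Purple (range 17 to 47) and about 2 ppm for Orange (range below 0.02 to 15).

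The Executive Summary says that the exposure index will take account of the earlier contamination: "Since there was a documented higher concentration of TCDD contamination prior to 1965". Among the factors for the index, Section V.G(1) also notes that "yearly records are available that reflect the amount of each herbicide sprayed".

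**The concern.** Read by its dates of use, Section II.B places only Orange, among the TCDD-containing herbicides, in the 1965 spraying. That would give 1965 the same D as the later years. Section V.G(1) instead gives it half the pre-1965 value, because of what was on hand and without saying how much of it was sprayed.

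The stake is the ordering of men within the exposed group. Section V.F(2) treats a positive correlation between exposure and findings as suggesting a disease syndrome. Section VI.H says that a regression of mortality or morbidity on the index would strengthen the case that a group difference is a herbicide effect and not bias. D is the only term for which the protocol fixes a scoring scale; Section V.G(2) says that values for crew position and route are still lacking. If the 1965 score is wrong, men with 1965 tours are misplaced relative to men with similar later tours.

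**Working it through.** **Inputs.** From Section V.G(1): D = 32, 16 and 2, and the stated factor of 16. The printed scale runs year and value together, but 32/2 confirms this reading. From Section II.B: archived means of 33 and 2 ppm; the highest Orange sample, 15 ppm; Orange with 96% of the 2,4,5-T and the other three with 4%; the other three with about 40% of the TCDD, which leaves about 60% for Orange.

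**Step 1: reproduce the stated factor.**

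- Scale: 32/2 = 16.0.
- Archived means: 33/2 = 16.5.
- Mass balance, TCDD per unit of 2,4,5-T: (40%/4%) / (60%/96%) = 10/0.625 = 16.0.

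The contrast between the two end values agrees with the rest of the protocol. The mass balance supports the ratio only, not the absolute levels.

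**Step 2: what the value 16 implies.** Let s be the share of high-dioxin product in the 2,4,5-T herbicide used in 1965. Blue and White contain no 2,4,5-T, and term P deals with their share. Then

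D = 32s + 2(1 − s).

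Setting D = 16 gives s = (16 − 2)/(32 − 2) = 14/30 = 46.7%. With 33 ppm in place of 32, s = 14/31 = 45.2%. The value 16 also lies just above the highest archived Orange sample (15 ppm), so it cannot stand for Orange alone. It is close to the scale midpoint, (32 + 2)/2 = 17, so it may have been meant as a rough equal mix.

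**Step 3: size of the possible excess in D.** The protocol gives no value of s, so every row below is an assumption. The first corresponds to the dates in Section II.B read strictly.

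| Assumed s | D for 1965 | 16 / D |
|---|---|---|
| 0 | 2.0 | 8.0 |
| 1/12 | 4.5 | 3.6 |
| 10% | 5.0 | 3.2 |
| 2/12 | 7.0 | 2.3 |
| 25% | 9.5 | 1.7 |
| 46.7% | 16.0 | 1.0 |
| 50% | 17.0 | 0.94 |

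The excess falls quickly once some carry-over is allowed, and disappears only near an equal mix.

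**The case against.** The strongest reply is that stock on hand and herbicide sprayed are different things, and that Orange starts in early 1965, not on 1 January. A changeover with old drums still being used at the start of the year fits both sections. This stands. A reader might infer that the two sections flatly contradict each other, or that 1965 tours are over-scored 8-fold; the documents support neither. Eight-fold is the limit reached when s = 0. The Executive Summary does not settle the matter, because the scale also ranks pre-1965 highest.

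A reader might also infer that the exposure index itself is wrong by the same factor and that its slope is flattened. The form of f is not specified, so an error in D passes through in full only if D enters as a multiplier. The protocol gives no count of men with 1965 tours. Section V.B(1)(a) says that the 1965 flight-line maintenance men may not be identifiable, and Table 5 marks August 1964 to December 1966 as uncertain. On the other side, Section II.B says that the change to Orange came with growth from four rotating aircrews to 30 permanent ones, so the 1965 group need not be negligible. Distortion of the slope is possible but not shown.

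Nor does Section V.G(2) say that the fallback crude index uses 32, 16 and 2. It refers to the TCDD concentration of the herbicides used each year, which is closer to the remedy proposed here.

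Finally, the index is a supporting tool. The RANCH HAND versus control rate comparisons that Section VI.A treats as central do not use D. That limits the severity. It does not supply a basis for the value 16.

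**Conclusion.** The concern holds in a limited form. The 1965 value of D is unsupported: it needs a high-dioxin share of about 47%, while the protocol's dates of use point to a share at or near zero and no share is stated anywhere. Term D for 1965 could be too high by anything up to 8-fold, depending on carry-over that the protocol does not quantify. This calculation takes the end values 32 and 2 as given and treats 1965 as a mixture of the two.

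The consequence is confined to the dose-response among RANCH HAND men, and its size there cannot be computed without the form of f and the number of men with 1965 tours. The documents do not show which section is right. Severity is moderate: a correctable input to a supporting analysis, not a defect in the main comparison.

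**What to change.** Reconcile Section V.G(1) with Section II.B, and state which of the 2,4,5-T herbicides were sprayed in 1965 and in what amounts. Replace the fixed value 16 with the mean TCDD concentration of those herbicides, weighted by the amounts recorded for that year. If the records show only Orange, 1965 takes the Orange value; if they show old stock, it enters by its recorded share. Use the same yearly values in the crude index of Section V.G(2). No particular form of f is required for this.

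The yearly records are already planned for term P, and the archived means for Purple and Orange are already cited. The protocol cites no archived mean for Pink or Green, so if either appears in the 1965 records, the concentration assumed for it should be stated.

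The cost is a protocol wording change and a small tabulation, with no new data collection. It should be done before the index is computed, because a change to D after outcomes are known would look post hoc.
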